Secondary

To determine the effectiveness of 6 months closed-loop compared with manually determined insulin dosing on glucose control, psychosocial well-being, sleep, cognitive functioning, ECG and health economics measures in adults with type 1 diabetes.

Section 3: Study Methods

Trial design

HCL-Adult is a multicentre, open label, parallel-group, superiority randomized clinical trial with equally sized treatment groups.

The intervention will last for 26 weeks, with an additional minimum 5 week period of active run-in which includes education (pre-randomisation). The exact duration of run-in will depend on individual training requirements. The study flow is presented in Figure 1.

Randomization

Group allocation (HCL or continuing standard care) will be random with a 1:1 ratio using minimization with 3 stratification variables, all of which are expected to be highly prognostic of primary outcome. These minimization variables are: 1) % time in target range pre-randomisation (dichotomised into <= 55% and > 55%); 2) study centre (7 sites); and 3) insulin delivery modality at enrolment (MDI or IPT). Due to the nature of the intervention, blinding of participants and investigators is not possible.

Sample size

Sample size calculation is based on a parallel design with 2 equally sized groups.

Assumptions used were derived from JDRF CGM randomized clinical trials [8, 9] that recruited a sample of 69 adults (25-70 years old) with type 1 diabetes and a baseline HbA1C < 10.5%, 86% of whom were using IPT and 14% using MDI. All participants had masked CGM data at randomization and at 6 months. Study investigator [name], personal communication, provided estimates of the effective standard deviation of percentage time spent in target glycaemic range at 6 months (adjusted for baseline) which was 9% (95% CI 8% to 12%) for pump users and 10% (95% CI 7% to 19%) for MDI users.

To detect a difference in percentage time in target glycaemic range of 5% with 80% power and 5% type I error rate assuming a common standard deviation of 9%, a total of 104 participants are needed. Allowing a drop-out rate of 10% a total of 120 people will be recruited, 60 randomized to HCL while 60 randomized to control group.

A more conservative scenario with a dropout rate of 20%, and unequal SDs of 12% and 19% for IPT and MDI users, respectively, increases the minimum detectable absolute difference to 9% with a power of 80%.

Framework

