This study is a superiority study with all analysis being performed on this basis.

Statistical interim analyses and stopping guidance

No interim analysis is planned. The study device has been previously proven to be safe for people with type 1 diabetes [10]; therefore, early stopping due to safety issues is not expected. However, safety recommendations will be made by an independent Data Safety Monitoring Committee (DSMC).

Timing of final analysis

The primary outcome and secondary glucose outcomes will be analysed collectively at the conclusion of the study. Other secondary outcomes will be analysed separately at the end of the study.

Health economic outcome and biomarkers will be analysed at a later date after additional funding is obtained.

Timing of outcome assessments

Pre-randomisation outcomes are collected at Visits 3-6, mid-study outcomes are collected at Visits 9-11 and end-of-study outcomes are collected at Visits 12-15 (Figure 1)

[figure not shown]

Figure 1: Study flow and timing of outcome assessments

Section 4: Statistical principles

Confidence intervals and p values

All hypothesis testing will be two-sided with an α of 0.05, with reported 95% confidence intervals.

No corrections for multiplicity are planned to control Type I error; rather, the effectiveness of the intervention will be assessed based on the clearly specified primary outcome; secondary outcomes are exploratory in nature and will be labelled as such in publications arising from the study. A transparent approach to reporting results will be taken, with the list of all pre-specified secondary outcomes included in every publication resulting from this study (this list would include a reference to relevant publication if results already published).

Results will be interpreted in light of the number of comparisons and where multiple comparisons indicate multiple effects, the consistency of these results will be discussed.

Adherence and protocol deviation

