Section 6 Analysis

Primary outcome

Outcome definition

Primary outcome is the percentage of time spent in target glucose range (3.9-10 mmol/L) measured by masked CGM over 3 weeks starting at 23 weeks post randomization (\pm 3 weeks) (glucose measured at 5-min intervals). Participants with a low number of available CGM readings in one or more weeks will have the CGM repeated and may have up to 5 weeks of masked CGM collection. To accurately represent participant's glycaemic status, only days with at least 70% valid CGM readings will be used (>= 202 valid readings) [11]. The percentage of time spent in target glucose range will be calculated by dividing the number of sensor readings falling in the range 3.9 – 10 mmol/L by the total number of sensor readings and multiplying by 100 over the whole period of masked CGM collection. If the participant has less than 10 representative days [11] their outcome will be counted as missing (individual glucose values will not be imputed).

Analysis methods

To test for an effect of the treatment group on the primary outcome, an ANCOVA including treatment arm and baseline percent time in target range will be conducted. The primary outcome will be analysed on an intention-to-treat basis on the entire study population with missing outcome data imputed using multiple imputations under missing at random (MAR) assumption (overall time in range will be imputed rather than single glucose values, see section on Missing data).

Results will be presented as the mean difference in the percent time in target range between treatment arms at the end of the study with 95% confidence interval and p value.

Model residuals will be visually inspected to test the assumptions of the model. In the event of violations to homoscedasticity and non-normal distribution, the outcome will be transformed using a natural logarithm. If the ANCOVA model still displays poor fit, non-parametric analysis (Wilcoxon rank sum test) will be employed.

Sensitivity analyses

- 1. ANCOVA with adjustment for factors used in the minimisation will be conducted (study centre 7 categories, insulin delivery modality 2 categories).
- 2. Replication of primary outcome analysis in complete case population (missing completely at random (MCAR) assumption)
- 3. Replication of primary outcome analysis in full study sample using multiple imputation of missing data under missing not at random (MNAR) assumption (see section Missing data)

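### The primary ANCOVA leaves out two minimisation factors, study centre and insulin modality; so far as they predict outcome beyond baseline, its standard error is overstated and precision is forgone

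*SAP*

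**What the plan says.** SAP Section 3, Randomization, describes 1:1 allocation by "minimization with 3 stratification variables, all of which are expected to be highly prognostic of primary outcome". The three are pre-randomisation time in range (split at 55%), study centre (7 sites) and insulin delivery modality at enrolment (MDI or IPT).

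Section 6, Primary outcome, Analysis methods, fixes the primary model: "an ANCOVA including treatment arm and baseline percent time in target range will be conducted". Baseline time in range therefore enters, but centre and modality do not.

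Those two appear in the first item under Sensitivity analyses: "ANCOVA with adjustment for factors used in the minimisation will be conducted (study centre 7 categories, insulin delivery modality 2 categories"). Modality also enters the planned interaction model, which addresses a different question. No reason is given for leaving the two factors out of the headline model.

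The Missing data section imputes separately by arm. It selects baseline and mid-study variables according to their correlation with the outcome, so neither factor is certain to be in the imputation model.

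**The concern.** Minimisation makes the arms more alike on centre and modality than simple randomisation would. If those factors affect the outcome, the true sampling variability of the treatment difference falls. A model that omits them does not see this, because it still counts their contribution as residual noise. The reported standard error is then larger than the true one, the 95% interval is too wide, and the nominal 5% test rejects a true null less than 5% of the time.

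At stake is the precision of the headline estimate. The trial constrains its allocation on these factors but does not use them in the result on which effectiveness will be judged. The model that matches the allocation is already written, but as a sensitivity analysis, so its interval and p value cannot be the primary result.

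**Working it through.** **Inputs from the SAP**

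- Test: "All hypothesis testing will be two-sided with an α of 0.05" (Section 4).
- Target: "To detect a difference in percentage time in target glycaemic range of 5% with 80% power and 5% type I error rate" (Section 3, Sample size).
- SD and evaluable number: "assuming a common standard deviation of 9%, a total of 104 participants are needed".
- Source of the SD: "at 6 months (adjusted for baseline) which was 9% (95% CI 8% to 12%) for pump users", and 10% for MDI users. These are adjusted for baseline and given within modality.
- Recruitment: "Allowing a drop-out rate of 10% a total of 120 people will be recruited".

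**Step 1. Reproduce the planned sample size**

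Normal approximation: n per arm = 2 × (1.960 + 0.842)² × 9² / 5² = 50.9, so 51 per arm and 102 in total. With the exact noncentral t distribution, 52 per arm gives 80.1% power, which matches the stated 104. Dropout: 104 / 0.9 = 115.6, so 116; the plan recruits 120.

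**Step 2. What theory predicts**

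Let f be the share of residual variance, given baseline, that centre and modality explain.

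- The planned model reports SE ≈ 9 × √(2/52) = 1.765, whatever f is.
- With perfect balance on the two factors, the true SE is 1.765 × √(1 − f).
- The reported SE is then too large by a factor 1/√(1 − f), and type I error is P(|Z| > 1.96/√(1 − f)).

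This gives 4.4% at f = 5%, 3.9% at 10%, 2.8% at 20% and 1.9% at 30%. Minimisation balances imperfectly, so actual values lie between these and 5%.

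**Step 3. Simulation with minimisation**

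There were 4,000 trials per setting, with n = 104 and a residual SD of 9 given baseline. Assumptions not in the SAP: minimisation probability 0.8, equal-sized centres, half MDI and half IPT, baseline SD 12, baseline slope 0.6, and f split equally between centre and modality. The SE columns are model-based means from the null runs. Power is for a 5-point difference.

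| f (assumed) | SE, planned | SE, adjusted | Type I, planned | Type I, adjusted | Power, planned | Power, adjusted |
|---|---|---|---|---|---|---|
| 0% | 1.76 | 1.77 | 4.8% | 4.6% | 79.9% | 79.5% |
| 5% | 1.77 | 1.74 | 5.0% | 5.1% | 80.4% | 81.2% |
| 10% | 1.77 | 1.69 | 4.1% | 5.0% | 80.2% | 83.0% |
| 20% | 1.77 | 1.59 | 2.9% | 4.5% | 81.7% | 87.1% |
| 30% | 1.77 | 1.49 | 2.5% | 5.2% | 83.5% | 91.6% |

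At 10%, 20% and 30%, the empirical SE of the planned estimate was about 1.68–1.71, 1.59–1.63 and 1.53. The reported SE was thus about 3–5%, 9–11% and 16% too large.

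The Monte Carlo error of a 5% rate is √(0.05 × 0.95 / 4000) = 0.34 points. A separate run with n = 104 and the same minimisation probability gave type I errors of 4.0%, 3.2% and 2.4% at 10%, 20% and 30%. At 5%, the departure from nominal is too small to resolve here; Step 2 bounds it at 4.4%.

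**Step 4. How large is f in points of time in range?**

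With equal groups, a modality gap g contributes variance g²/4. If modality alone carried f, then g = 2 × 9 × √f: 4.0, 5.7, 8.0 and 9.9 points at 5%, 10%, 20% and 30%. Split equally with centre, g is 4.0, 5.7 and 7.0 points at 10%, 20% and 30%, with between-centre SDs of 2.0, 2.8 and 3.5.

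**The case against.** **The loss is conditional.** Prognostic of the outcome does not mean prognostic given baseline. Baseline time in range is itself a minimisation factor, enters as a continuous covariate, and may already carry much of any centre or modality difference. Step 4 shows that the upper part of the assumed range needs baseline-adjusted modality gaps as large as or larger than the 5-point treatment effect. This stands, and for that reason the point is stated conditionally.

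**The adjusted model is already prespecified.** Readers will see both estimates. That is true, but the headline interval and p value still come from the baseline-only model.

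**Stronger readings that the SAP does not support**

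- *The primary analysis is invalid.* No bias arises, and the test errs on the conservative side.
- *The planned 80% power fails.* In Step 3 the planned model keeps about 80% or more throughout. A reader might reply that the 9% SD is a within-modality figure, so a modality gap would raise the planned model's residual SD to √(81 + g²/4). For assumed gaps of 4, 6 and 8 points that is 9.2, 9.5 and 9.8, and a simulation on that basis gave planned-model power of about 78%, 77% and 74%. But the SAP reports no modality gap beyond baseline, so a shortfall is possible, not demonstrated.
- *Every secondary ANCOVA should change too.* That was not examined, and the SAP labels those outcomes exploratory.

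**Practical limits.** Imputation by arm with about 60 per arm leaves roughly 60 / 7, or 8 to 9, participants per centre, and the simulations did not include multiple imputation. An open-ended option to pool small centres would add analyst discretion. Both limits stand and shape the fix.

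**Conclusion.** The mismatch between allocation and primary analysis is plain on the face of the SAP, and the direction of its effect is certain if centre or modality matters beyond baseline. Its size is not known from the document. At 10% to 30% of residual variance explained, the planned test runs at about 4.0% down to 2.4%, and adjustment gains roughly 3 to 8 points of power. At 5% the gain is about 1 point and type I error is close to nominal. At 0% adjustment costs about 1 point of power or less.

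These figures rest on the assumed share and on the simulation settings listed above, with complete data on 104 participants. This is an efficiency and calibration point: worth acting on because the downside is negligible, but not a threat to the validity of the trial.

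**What to change.** - **Primary model.** Fit treatment arm, continuous baseline percent time in range, insulin modality and study centre. State explicitly that continuous baseline is retained, since the wording of sensitivity analysis 1 names only centre and modality.
- **Sensitivity.** Move the baseline-only ANCOVA to the sensitivity list.
- **Imputation.** Include modality and centre in the imputation model for the primary outcome whatever their observed correlation with it, so that it matches the analysis model.
- **Small centres.** If pooling may be needed, fix the rule and its threshold in advance, without sight of outcomes by arm.

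**Cost.** Seven extra parameters (six for centre, one for modality): with 104 evaluable, residual degrees of freedom fall from 104 − 3 = 101 to 104 − 10 = 94. No new data are needed. The SAP text changes; if the protocol, which is not shown, also fixes the primary model, it must be aligned.

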All secondary outcomes (except fasting capillary blood glucose and number of hypoglycaemic events) will be analysed using ANCOVA including treatment and baseline score of the outcome. Where the distribution of residuals is heteroscedastic even after logarithmic transformation, a Wilcoxon rank sum test will be performed (in which case no adjustments for baseline will be performed). With parametric methods, mean differences with 95% CI will be presented, whereas with non-parametric methods, median difference with 95% CI will be presented ([13]).

A mixed effects linear regression will be used to analyse fasting capillary blood glucose with random intercepts for individuals and study arm as a fixed effect.

The number of hypoglycaemic events will be analysed using Poisson regression or negative binomial regression if overdispersion is apparent.

Percent time in ranges, mean glucose, standard deviation and coefficient of variation will be performed separately for day (6:00 – 23:59) and night (0:00 – 5:59).

All analyses will be performed separately for mid-study and end-of-study data.

Sensitivity analysis

Due to exploratory nature of the outcomes, no sensitivity analysis will be performed.

Subgroup analysis

To estimate the effect of the intervention based on regimen (IPT or MDI), a treatment group by regimen interaction will be included in all models. Where non-parametric analysis will be performed, each regimen will be analysed separately.

2. Clinical outcomes

Outcome definition

- Change in average total daily dose of insulin and basal/bolus proportions taken over the last 7 days
- Change in insulin-to-carbohydrate ratio (ICR) (ICR is usually expressed in 1:X form where X represents grams of carbohydrates covered by 1 unit of insulin. This ratio can be constant throughout the day or can vary for breakfast, lunch and dinner times. It will be analysed separately for breakfast, lunch and dinner time, as well as a weighted average overall for the day)
- Change in body weight (kg)

All clinical outcomes are measured at randomisation, mid-study and end-of-study.

Analysis method

Linear regression will be used to evaluate the effect of treatment arm on the change score from baseline. Where the distribution of residuals is heteroscedastic even after logarithmic transformation, rank sum test will be performed.

All analysis will be performed separately for mid-study and end-of study.

Sensitivity analysis

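### The primary analysis can switch, on a reading of residual plots, to a log model and then to an unadjusted rank test, neither of which estimates the promised mean difference

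*SAP*

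**What the plan says.** SAP Section 6 (Primary outcome, Analysis methods) specifies ANCOVA on treatment arm and baseline time in range. The result is to be given as a mean difference between arms with a 95% confidence interval and p value. Residuals are judged by eye, and two fallbacks follow in order. The first changes the scale: "In the event of violations to homoscedasticity and non-normal distribution, the outcome will be transformed using a natural logarithm". The second changes the test, and is taken when the first has not cured the problem, again without a numerical threshold: "If the ANCOVA model still displays poor fit, non-parametric analysis (Wilcoxon rank sum test) will be employed".

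The primary section does not say what is estimated or reported after either step, or that the second step loses the baseline adjustment. The section on secondary glucose outcomes is open about that loss: "a Wilcoxon rank sum test will be performed (in which case no adjustments for baseline will be performed". It also names a median difference with a 95% confidence interval as the estimate for non-parametric analyses.

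Section 3 (Sample size) plans to find a difference of 5 points between the arms and gives these figures: "5% type I error rate assuming a common standard deviation of 9%, a total of 104 participants are needed". The SD behind this is a baseline-adjusted one: "adjusted for baseline) which was 9% (95% CI 8% to 12%) for pump users". Section 4 fixes the test level: "All hypothesis testing will be two-sided with an α of 0.05, with reported 95% confidence intervals". It rests the judgement of effectiveness on the single primary outcome and calls the secondary outcomes exploratory.

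**The concern.** The trial has one confirmatory result, and its scale, test and estimate can change after someone has looked at residual plots, with no stated threshold. Three things follow.

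1. **The estimate changes without being redefined.** A log-scale ANCOVA gives a ratio of geometric means. A rank sum test gives no mean difference. The sentence promising a mean difference in percentage points can be honoured in only one of the three branches.
2. **The log step suits the outcome badly.** Time in range is a percentage bounded at 100. If it is roughly symmetric or left-skewed, taking logs stretches the lower tail. That can create the poor fit that triggers the second step.
3. **The rank sum test gives up the planned precision.** The sample size relies on an SD from which baseline variation has already been removed. An unadjusted test works with the larger raw SD.

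**Working it through.** **Inputs from the SAP.** Difference 5 points; baseline-adjusted SD 9%; two-sided alpha 0.05; power 80%; 104 evaluable; 120 recruited with 10% dropout, so 120 × 0.9 = 108, or 54 per arm.

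**Inputs not in the SAP (assumed).** The correlation r between baseline and 6-month time in range, taken as 0.3 to 0.7. The only support is qualitative: Section 3 (Randomization) expects the minimisation variables, which include baseline time in range, to predict the outcome strongly. The error shapes, and the mean of 60 and SD of 12 to 15 in the skewness check, are also assumed.

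**Step 1: the plan's own figure.** n per arm = 2 × (1.960 + 0.842)² × 9² / 5² = 50.9, so 51. The t-based version gives 51.84, so 52 per arm and 104 in total. The stated figure is reproduced.

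**Step 2: power of the planned ANCOVA.** Power = Φ(5 / (9 × √(2/n)) − 1.96).
- n = 52: Φ(2.833 − 1.96) = 80.9%
- n = 54: Φ(2.887 − 1.96) = 82.3% (t-based 81.6%)

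Simulation at 54 per arm gives 80-83%. I use about 81%.

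**Step 3: power of the unadjusted rank sum test.** Without the covariate, the SD becomes 9 / √(1 − r²). For normal errors the rank test has relative efficiency 3/π = 0.955, so n is replaced by 54 × 0.955 = 51.6. For r = 0.5, the SD is 10.39 and power = Φ(5 / (10.39 × √(2/51.6)) − 1.96) = Φ(0.483) = 68.5%.

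| Assumed r | Raw SD | Formula, normal, 54 per arm | Simulated, normal, 54 per arm | Simulated, left-skewed, 52 per arm | Simulated, t with 4 df, 52 per arm |
|---|---|---|---|---|---|
| 0.3 | 9.43 | 76.8% | 74% | – | – |
| 0.5 | 10.39 | 68.5% | 66% | 76% | 78% |
| 0.6 | 11.25 | 61.7% | 62% | 69% | 70% |
| 0.7 | 12.60 | 52.2% | 51% | 59% | 61% |

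ANCOVA power in the 52-per-arm skewed and heavy-tailed runs was 79-82%. At 54 per arm, skewed and t4 errors over r = 0.5 to 0.7 gave rank-test power of 52-79%, and at r = 0.3 they gave no loss.

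**Step 4: the log transformation.** For an approximately normal percentage with mean 60, skewness before the log is about 0. After it, skewness is about −0.7 at SD 12 and about −1.1 at SD 15.

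**The case against.** The best defence is that the fallback is used only when residuals are poor, which is where a rank test is at its most efficient. A power loss computed under normal errors then describes the wrong case. Much of this stands. With strongly left-skewed (reflected exponential) errors and 54 per arm, ANCOVA and rank-test power were 81% and 82% at r = 0.5, but 81% and 56% at r = 0.7. With t errors on 3 df they were 84% and 81% at r = 0.5, and 84% and 59% at r = 0.7. At r = 0.3 the rank test was the stronger in both settings (93% against 82-84%). The loss therefore runs from none to large. A reader might infer a fixed fall to 50-70%, but the SAP gives neither r nor the error shape, so it does not support that.

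The skewness illustration starts from a symmetric outcome, which would not itself prompt a transformation for non-normality. It shows only that the log works in the wrong direction for symmetric or left-skewed data; a right-skewed outcome would be different.

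It may also be said that unequal variances call for some remedy. With 54 per arm and SDs of 6 v 12 or 5 v 15, the ordinary t test rejected 5.0-5.2% under the null, so unequal variances between equal arms alone do not. That check does not cover variance that changes with baseline, or non-normality.

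Four further readings are tempting but not supported:

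- *That the effect could no longer be expressed in percentage points.* A median difference on the untransformed outcome is in those units, and the SAP names one for secondary glucose outcomes. The primary section simply does not adopt it.
- *That the primary regimen interaction would be lost.* The planned subgroup analysis of the primary outcome is a linear regression with an interaction term and has no non-parametric branch. The rule "Where non-parametric analysis will be performed, each regimen will be analysed separately" stands under secondary outcomes.
- *That the analyst inspects unblinded data.* Section 3 says participants and investigators cannot be blinded; it is silent on the analyst.
- *That every secondary outcome needs the same remedy.* Those outcomes are exploratory, and for the glucose outcomes the loss of adjustment is disclosed. A rank method may be reasonable for very low glucose ranges with many zeros.

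**Conclusion.** The point holds for the primary outcome. The confirmatory analysis can move, on a subjective reading of plots, from a baseline-adjusted mean difference to a log-scale model and then to an unadjusted rank sum test. Neither alternative estimates the promised quantity, and no substitute is named. This part rests on the text alone.

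The size of the power loss rests on assumptions. With 54 per arm, a 5-point effect and adjusted SD 9%, it is a fall from about 81% to about 66-51% for r = 0.5 to 0.7 with normal errors, or 15 to 30 points. With the left-skewed and t4 errors simulated, power is about 52-79% over the same r. At r near 0.3 the loss is about 5 to 7 points with normal errors and nil with skewed or heavy-tailed errors. It arises only if the fallback is triggered.

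**What to change.** In Section 6, Primary outcome:

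1. State one primary analysis: ANCOVA on the percentage scale with treatment arm and baseline time in range, using HC3 or bootstrap standard errors whatever the residual plots show. Report the mean difference in percentage points.
2. Delete the log step for the primary outcome.
3. Keep any rank-based analysis only as a labelled sensitivity analysis, preferably baseline-adjusted (rank ANCOVA), and name the estimate it reports.

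The clause in the Missing data section that replaces missing values by the arm median when non-parametric methods are used would then no longer affect the primary analysis.

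The cost is SAP wording only. Robust or bootstrap intervals may be marginally wider when the model assumptions hold. No change to the secondary-outcome methods is needed for this point.
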